### **12.1.1.2 Serious adverse event**

Once it is determined that a subject experienced an AE, the seriousness of the AE must be determined. An SAE must meet 1 or more of the following criteria:

- Death
- Life-threatening
- (Life-threatening does not include a reaction that might have caused death had it occurred in a more severe form.)
- Significant or persistent disability/incapacity
- Congenital anomaly/birth defect (including that occurring in a fetus)
- Important medical event that, based upon appropriate medical judgment, may jeopardize the patient or subject and may require medical or surgical intervention to prevent 1 of the other outcomes listed in the definition of serious
- (Important medical events may include, but are not limited to, potential Hy's Law [see Section 12.2], allergic bronchospasm requiring intensive treatment in an emergency room or at home, blood dyscrasias that do not result in inpatient hospitalization, or the development of drug dependency or drug abuse.)
- Initial inpatient hospitalization or prolongation of hospitalization
- (A subject admitted to a hospital, even if he/she is released on the same day, meets the criteria for the initial inpatient hospitalization. An emergency room visit that results in admission to the hospital would also qualify for the initial inpatient hospitalization criteria. However, emergency room visits that do not result in admission to the hospital would not qualify for this criteria and, instead, should be evaluated for 1 of the other criteria in the definition of serious [eg, life-threatening adverse experience, important medical event].
- Hospitalizations for reasons not associated with the occurrence of an AE [eg, preplanned surgery or elective surgery for a pre-existing condition that has not worsened or manifested in an unusual or uncharacteristic manner] do not qualify for reporting. For example, if a subject has a condition recorded on his/her medical history and later has a preplanned surgery for this condition, it is not appropriate to record the surgery or hospitalization as an SAE, since there is no AE upon which to assess the serious criteria. Please note that, if the pre-existing condition has worsened or manifested in an unusual or uncharacteristic manner, this would then qualify as an AE and, if necessary, the seriousness of the event would need to be determined.)

#### **12.1.1.2.1 Anticipated serious adverse events**

The following Anticipated SAEs are anticipated to occur in the population studied in this protocol at some frequency that is independent of drug exposure.

This list does not change the investigator's obligation to report all SAEs (including Anticipated SAEs) as detailed in Section 12.1.2.3.

**Table 12-1: Anticipated serious adverse events for CIDP population**

Neurologic diseases a :	muscle weakness, numbness and pain in the extremities, impaired balance, difficulty walking
------------------------------------	---

a The investigator should report these adverse events as serious adverse events only if they meet criteria for seriousness (see Section 12.1.1.2).

### **12.1.1.3 Adverse events of special interest**

An AE of special interest is any AE that a regulatory authority has mandated be reported on an expedited basis, regardless of the seriousness, expectedness, or relatedness of the AE to the administration of a UCB product/compound.

Potential Hy's Law, defined as  $\geq 3$  xULN ALT or AST with coexisting  $\geq 2$  xULN total bilirubin in the absence of  $\geq 2$  xULN ALP, with no alternative explanation for the biochemical abnormality, must ALWAYS be reported to UCB as an AE of special interest (ie, without waiting for any additional etiologic investigations to have been concluded). Follow-up information should then be reported if an alternative etiology is identified during investigation and monitoring of the subject.

### **12.1.1.4 Adverse events of interest**

For rozanolixizumab, AEs of interest that require immediate reporting to UCB are:

- Severe headache
- Moderate to severe diarrhea
- Moderate to severe abdominal pain
- Moderate to severe vomiting

These events should be reported to UCB within 24 hours, regardless of seriousness, using the fax and email details for AEs of interest and independent of SAE reporting.

Additional assessments which may be required in case of AEs of interest are presented in [Table 5-2](#).

### **12.1.2 Procedures for reporting and recording adverse events**

The subject will be given the opportunity to report AEs spontaneously. A general prompt will also be given at each study visit to detect AEs. For example:

“Did you notice anything unusual about your health (since your last visit)?”

In addition, the investigator should review any self-assessment procedures (eg, e-diary) employed in the study.

#### **12.1.2.1 Description of adverse events**

When recording an AE, the investigator should use the overall diagnosis or syndrome using standard medical terminology, rather than recording individual symptoms or signs. The eCRF and source documents should be consistent. Any discrepancies between the subject's own words

on his/her own records and the corresponding medical terminology should be clarified in the source documentation.

Details for completion of the Adverse Event eCRF (including judgment of relationship to IMP) are described in the eCRF Completion Guidelines.

For recording an AE, Common Terminology Criteria for Adverse Events (CTCAE) will be used, and only if it is impossible to assess severity using CTCAE, then AE intensity will be assessed using a scale of mild, moderate, or severe.

### **12.1.2.2 Rule for repetition of an adverse event**

An increase in the intensity of an AE should lead to the repetition of the AE being reported with:

- The outcome date of the first AE that is not related to the natural course of the disease being the same as the start date of the repeated AE, and the outcome of “worsening”
- The AE verbatim term being the same for the first and repeated AE, so that the repeated AE can be easily identified as the worsening of the first one

### **12.1.2.3 Additional procedures for reporting serious adverse events**

If an SAE is reported, UCB must be informed within 24 hours of receipt of this information by the site (see contact information for SAE reporting listed in the Serious Adverse Event Reporting section at the front of the protocol). The investigator must forward to UCB (or its representative) a duly completed “Investigator SAE Report Form for Development Drug” (SAE report form) provided by UCB, even if the data are incomplete, or if it is obvious that more data will be needed in order to draw any conclusions. Information recorded on this form will be entered into the global safety database.

An investigator SAE report form will be provided to the investigator. The investigator SAE Report form must be completed in English.

It is important for the investigator, when completing the SAE report form, to include the assessment as to a causal relationship between the SAE and the IMP administration. This insight from the investigator is very important for UCB to consider in assessing the safety of the IMP and in determining whether the SAE requires reporting to the regulatory authorities in an expedited manner.

Additional information (eg, autopsy or laboratory reports) received by the investigator must be provided within 24 hours. All documents in the local language must be accompanied by a translation in English, or the relevant information included in the same document must be summarized in the investigator SAE report form.

The investigator is specifically requested to collect and report to UCB (or its representative) any SAEs (even if the investigator is certain that they are in no way associated with the IMP), up to 30 days from the end of the study for each subject, and to also inform participating subjects of the need to inform the investigator of any SAE within this period. Serious AEs that the investigator thinks may be associated with the IMP must be reported to UCB regardless of the time between the event and the end of the study.

Upon receipt of the SAE report form, UCB will perform an assessment of expectedness of the reported SAE. The assessment of the expectedness of the SAE is based on the IB.

#### **12.1.2.4      Immediate reporting of adverse events**

The following AEs must be reported immediately using the SAE Report Form according to the procedure in Section 12.1.2.3:

- SAE: AE that the investigator classifies as serious by the above definitions regardless of causality
- Suspected transmission of an infectious agent via a medicinal product
- AE of special interest (see Section 12.1.1.3)
- AE of interest (see Section 12.1.1.4)
- Confirmed LTBI, active TB, and NTMBI (see Section 12.3.7)

#### **12.1.3      Follow up of adverse events**

An AE should be followed until it has resolved, has a stable sequelae, the investigator determines that it is no longer clinically significant, or the subject is lost to follow up. This follow-up requirement applies to AEs, SAEs, and AEs of special interest; further details regarding follow up of PDILI events is provided in Section 12.2.1.4.

If an AE is ongoing at the end of the study for a subject, follow up should be provided until resolution/stable level of sequelae is achieved, or until the investigator no longer deems that it is clinically significant, or until the subject is lost to follow up. If no follow up is provided, the investigator must provide a justification. The follow up will usually be continued for 12 weeks after the subject has discontinued his/her IMP.

Information on SAEs obtained after clinical database lock will be captured through the Patient Safety (PS) database without limitation of time.

#### **12.1.4      Pregnancy**

If an investigator is notified that a subject has become pregnant after the first intake of any IMP, the investigator must immediately notify UCB's PS department by providing the completed Pregnancy Report and Outcome form (for contact details see SAE reporting information at the beginning of this protocol). The subject should be withdrawn from the study as soon as pregnancy is known (by positive pregnancy test), and the following should be completed:

- The subject should return for a PEOT Visit.
- The subject should immediately stop the intake of the IMP or be down-titrated as instructed at the PEOT Visit.
- A Final Visit should be scheduled 12 weeks after the subject has discontinued her IMP.

The investigator must inform the subject of information currently known about potential risks and about available treatment alternatives.

The pregnancy will be documented on the Pregnancy Report and Outcome form provided to the investigator. The progression of the pregnancy and the eventual birth (if applicable) must be followed up using the Pregnancy Report and Outcome form in which the investigator has to report on the health of the mother and of the child. Every reasonable attempt should be made to

follow the health of the child for 30 days after birth for any significant medical issues. In certain circumstances, UCB may request that follow up is continued for a period longer than 30 days. If the subject is lost to follow up and/or refuses to give information, written documentation of attempts to contact the subject needs to be provided by the investigator and filed at the site. UCB's PS department is the primary contact for any questions related to the data collection for the pregnancy, eventual birth, and follow up.

In cases where the partner of a male subject enrolled in a clinical study becomes pregnant, the investigator or designee is asked to contact the subject to request consent of the partner via the Partner Pregnancy Consent form that has been approved by the responsible IRB/IEC and should be available in the investigator site file. In case of questions about the consent process, the investigator may contact the UCB/contract research organization (CRO) contract monitor for the study. The investigator will complete the Pregnancy Report and Outcome form and send it to UCB's PS department (for contact details see SAE reporting information at the beginning of this protocol) only after the partner has agreed that additional information can be captured and has provided the signed Partner Pregnancy Consent form. UCB's PS department is also the primary contact for any questions related to the data collection for the partner pregnancy, eventual birth, and follow up.

A pregnancy becomes a SAE in the following circumstances: miscarriage, abortion (elective or spontaneous), unintended pregnancy after hormonal contraceptive failure (if the hormonal contraceptive was correctly used), ectopic pregnancy, fetal demise, or any congenital anomaly/birth defect of the baby. Those SAEs must be additionally reported using the investigator SAE Report form.

#### **12.1.5 Suspected transmission of an infectious agent via a medicinal product**

For the purposes of reporting, any suspected transmission of an infectious agent via a medicinal product should be considered as an SAE; such cases must be reported immediately, recorded in the AE module of the eCRF, and followed as any other SAE. Any organism, virus, or infectious particle (eg, prion protein transmitting transmissible spongiform encephalopathy), pathogenic or nonpathogenic, is considered an infectious agent.

#### **12.1.6 Overdose of investigational medicinal product**

Excessive dosing (beyond that prescribed in the protocol and including overdose ie, >10% above [REDACTED]) should be recorded in the eCRF. Any SAE or nonserious AE associated with excessive dosing must be followed as any other SAE or nonserious AE. These events are only considered AEs or SAEs if there are associated clinical signs and symptoms or if the act of taking the excess medicine itself is an AE or SAE (eg, suicide attempt).

#### **12.1.7 Safety signal detection**

Selected data from this study will be reviewed periodically to detect as early as possible any safety concern(s) related to the IMP so that investigators, clinical study subjects, regulatory authorities, and IRBs/IECs will be informed appropriately and as early as possible. A DMC will be responsible for monitoring safety data during the study. Further details are provided in Section 14.7.

The Study Physician or medically qualified designee/equivalent will conduct an ongoing review of SAEs and perform ongoing SAE reconciliations in collaboration with the PS representative.

As appropriate for the stage of development and accumulated experience with the IMP, medically qualified personnel at UCB may identify additional safety measures (eg, AEs, vital signs, laboratory or ECG results) for which data will be periodically reviewed during the course of the study.

### **12.1.8      Suicidality**

At Screening, the investigator will query each subject if he/she has a lifetime history of suicide attempt (including an active attempt, interrupted attempt, or aborted attempt) or suicidal ideation in the past 6 months. A full C-SSRS “Lifetime recent” assessment will be performed only when the subject has a positive response to this query. This scale will be assessed by trained study personnel. When suicide attempt or suicidal ideation is confirmed by a positive response (Yes) to either Question 4 or Question 5 of the C-SSRS, the subject must be excluded and immediately referred to a Mental Healthcare Professional.

At each clinical visit, the investigator must query the suicidal ideation since the last visit. A full C-SSRS “Since last visit” assessment will be performed only when the subject has a positive response to this query. When suicide attempt or suicidal ideation is confirmed by a positive response (Yes) to either Question 4 or Question 5 of the C-SSRS, the subject must be withdrawn and immediately referred to a Mental Healthcare Professional. Details of case must be documented by the investigator (PI or investigator physician, not site staff conducting the C-SSRS) and provided to UCB via the SAE reporting process.

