a Screening Visit will be performed between Day -35 and -14, the Screening Period continues until Day -1.

b One or two days after the subject's first 3 doses of IMP, the subject will be telephoned, and a healthcare professional will visit the subject at home to collect PK samples and immunoglobulins (total IgG and IgG subclasses) (only at Visit 7). Alternately, the visit can be conducted at the site as deemed necessary by site personnel and/or the subject.

c The following visits (9, 11, 13, 15, 18, and 20) will be performed by a healthcare professional visiting the subject at his/her home. Alternately, the visits can be conducted at the site as deemed necessary by site and/or subject. Feasibility of IMP dosing in a home setting will have to be confirmed before the visit is conducted (see Section 8.2).

d For eligibility criteria the lab data from Screening will be used. However, the urine pregnancy test at Visit 2 also must be negative for eligibility.

e On dosing visits prior to Visit 9 vital signs will be measured prior to IMP administration, at the end of the infusion, at 2 and 4 hours after the end of the infusion. From Visit 9, vital signs will be measured predose, at the end of the infusion and 2 hours after the end of the infusion only. At nondosing visits, vital signs need only be taken once during the visit. For subjects requiring additional assessments due to AEs (see Table 5-2), additional vital sign measurements may be taken based on the timing of the assessments.

f Body weight at screening will be used for calculation of the dose. Height will be assessed only at Screening.

g A full C-SSRS assessment will be performed only when subject has a positive response to the suicidal ideation query. If a subject has active suicidal ideation as confirmed by the answer 'Yes' to Question 4 or Question 5 of the C-SSRS assessments, the subject will be excluded or withdrawn from the study and immediately referred to a Mental Healthcare Professional.

h See requirements in Table 5-2 in case the subject experiences severe headache.

i Serology includes hepatitis C virus (HCV)-antibodies (Ab)+, hepatitis B virus antibodies (HBsAg and HBcAb), human immunodeficiency virus antibodies (HIV1 and HIV2).

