15. Subject has a history of clinically relevant ongoing chronic infections including but not limited to human immunodeficiency virus (HIV), hepatitis B, hepatitis C, or is tested positive for HIV (anti-HIV1 or anti-HIV2 antibodies), hepatitis B (HBsAg positive or HBcAb positive without positive HBsAb), or hepatitis C antibody (HCAb) at the Screening Visit.
16. Subjects with known TB infection, at high risk of acquiring TB infection, or latent tuberculosis infection (LTBI), or current/history of nontuberculosis mycobacteria (NTMB) are excluded.
  - a. Known TB infection whether present or past is defined as:
    - Active TB infection or clinical signs and symptoms suggestive of TB (pulmonary or extrapulmonary).
    - History of active TB infection involving any organ system or findings in other organ systems consistent with TB infection.
    - Any historical evidence by radiography or other imaging modalities consistent with previously active TB infection.
  - b. High risk of acquiring TB infection is defined as:
    - Known exposure to another person with active TB infection within the 3 months prior to Screening.
    - Time spent in a healthcare delivery setting or institution where individuals infected with TB are housed and where the risk of transmission of infection is high.
  - c. LTBI (see Section 12.3 for further details and instructions).

- 
- d. NTMB is defined as a group of lung infections caused by mycobacteria different from mycobacterium tuberculosis infections.
  - 17. Subject has a family history of primary immunodeficiency.
  - 18. Subject has a clinically relevant active infection (eg, sepsis, pneumonia, abscess) or has had a serious infection (resulting in hospitalization or requiring parenteral antibiotic treatment) within 6 weeks prior to the first dose of IMP.
  - 19. Subject has active neoplastic disease or history of neoplastic disease within 5 years of Screening Visit (except for basal or squamous cell carcinoma of the skin or carcinoma in situ of the uterine cervix which has been definitively treated with SOC approaches).
  - 20. Subject has a lifetime history of suicide attempt (including an active attempt, interrupted attempt, or aborted attempt), or has suicidal ideation in the past 6 months as indicated by a “yes” answer to numbers 4 or 5 on the screening Columbia Suicide Severity Rating Scale (C-SSRS).

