## 6.4 Withdrawal criteria

Subjects are free to withdraw from the study at any time, without prejudice to their continued care.

Subjects **MUST be withdrawn from the study** if any of the following events occur:

1. Subject withdraws his/her consent.
2. Subject becomes pregnant during the study, as confirmed by a positive pregnancy test.

Subjects **must discontinue IMP** if any of the following events occur:

1. Subject develops an illness that would interfere with his/her continued participation.
- Subject has a serious infective episode requiring hospitalization or iv antibiotic therapy (including but not limited to bacteremia or sepsis, bacterial meningitis, osteomyelitis or septic arthritis, bacterial pneumonia, or visceral abscess).
- Subject has an AE of severe infusion reaction requiring corticosteroid and/or epinephrine therapy (see Section 12.1.9).
- Subject has an AE of severe anaphylactic reaction requiring corticosteroid and/or epinephrine therapy.
- Subject has a TB test that is confirmed positive or any further evidence suggestive of potential TB infection (eg, exposure) and further examinations result in a diagnosis of active TB or LTBI (refer to Section 12.3.7 for further details and instructions).
- If a nontuberculosis mycobacterium infection (NTMBI) is identified during a study, the same withdrawal procedures as those used for an active TB infection identified during the study should be followed.
2. Subject has active suicidal ideation as indicated by a positive response (Yes) to either Question 4 or Question 5 of the “Since Last Visit” version of the C-SSRS. The subject should be referred immediately to a Mental Healthcare Professional.
3. The sponsor or a regulatory agency requests withdrawal of the subject.
4. Subject needs or takes PLEX, dexamethasone or rituximab.
5. Subject is treated with rescue medication and/or relapses during the Treatment Period (refer to Section 7.7.3).

Subjects **may be discontinued from IMP** at the discretion of the investigator, Medical Monitor, and Study Physician if any of the following events occur:

1. Subject takes prohibited concomitant medications during the Treatment Period as defined in this protocol (refer to Section 7.7.2).

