2. Subject experiences a severe AE of headache which is considered related to the IMP in the opinion of the investigator (see Section 12.1.10). Following an event of a severe headache, a subject may continue participation in the study if the subject is willing to do so and the investigator, Medical Monitor, and Study Physician agree that the subject’s continuation in

the study poses no significant risk for the subject. The use of symptomatic headache treatment is allowed at the discretion of the investigator. The IMP dose can be reduced to [REDACTED] (or its placebo equivalent) if the headache persists despite symptomatic treatment (refer to Section 12.1.10 for details on the medical management of headaches and Section 7.2 for treatment to be administered).

3. Subject experiences severe AE of gastrointestinal disturbance which is considered related to the IMP in the opinion of the investigator. Following an event of a severe gastrointestinal disturbance, a subject may continue in the study if they are willing to do so and the investigator and Medical Monitor agree that the subject's continuation in the study poses no significant risk

Subjects **may be withdrawn from the study** at the discretion of the investigator, Medical Monitor, and Study Physician if any of the following events occur:

1. Subject is noncompliant with the study procedures or medications in the opinion of the investigator.
2. In case of intake of prohibited concomitant medication other than IVIg, SCIG, PLEX, dexamethasone or rituximab, the investigator will (where possible) discuss with the Medical Monitor and/or Sponsor Study Physician and a decision will be made whether the subject should discontinue IMP.

Subjects who withdraw from the study or discontinue IMP during the Treatment Period should complete the assessments outlined for Visit 17/PEOT (see Table 5-1 and Section 8.4). Subjects who withdraw from the study and who are not entering the OLE will be encouraged to return to the clinic for all visits during the Observation Period (which should occur every 2 or 3 weeks ( $\pm 3$  days) following their final dose of IMP) and the Final Visit (scheduled 12 weeks after final dose of IMP). The subjects can return to their SOC during the Observation Period.

Investigators should attempt to obtain information on subjects in the case of withdrawal.

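### After the first dose, the suicidality query, the gate to the C-SSRS and the stopping rules all rest on ideation, so a suicide attempt without reported ideation triggers no mandatory suicidality action

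*Protocol*

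**What the plan says.** **Screening.** Protocol Section 12.1.8 has the investigator ask about lifetime attempts as well as recent ideation. Exclusion 20 (Section 6.2.3) lists an attempt as a separate ground for exclusion: "Subject has a lifetime history of suicide attempt (including an active attempt, interrupted attempt, or aborted attempt". It uses Questions 4 and 5 of the C-SSRS only for the ideation part.

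**On study, the query.** Section 12.1.8: "At each clinical visit, the investigator must query the suicidal ideation since the last visit".

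**On study, the gate.** Table 5-1 footnote g: "A full C-SSRS assessment will be performed only when subject has a positive response to the suicidal ideation query". Section 12.1.8 and SAP Section 10.4.3 set the same gate.

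**On study, the trigger.** The Section 6.4 list of mandatory IMP stops reads "Subject has active suicidal ideation as indicated by a positive response (Yes) to either Question 4 or Question 5", and footnote g uses the same criterion. Section 12.1.8 does name an attempt, but in this form: "When suicide attempt or suicidal ideation is confirmed by a positive response (Yes) to either Question 4 or Question 5 of the C-SSRS".

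**On study, the consequence.** Under Section 6.4 the patient must stop IMP and be referred at once. Under footnote g, "the subject will be excluded or withdrawn from the study and immediately referred to a Mental Healthcare Professional". Section 12.1.8 says the patient must be withdrawn, without saying from what.

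**The concern.** An attempt and a Yes to Question 4 or 5 are two different criteria in the sponsor's own exclusion list, yet only the second is carried past the first dose. A patient can have made an attempt, including an interrupted or aborted one, and still answer No when asked about ideation. The plan then has no suicidality rule that obliges anyone to stop IMP or refer the patient. The protocol allows that attempts can happen on study: Section 12.1.6 on overdose covers the case "if the act of taking the excess medicine itself is an AE or SAE (eg, suicide attempt". Because study personnel give the IMP, that mention is only secondary support.

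A smaller problem sits in the same rule. For one and the same answer, Section 6.4 stops treatment while footnote g ends study participation, so sites hold two instructions.

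**Working it through.** No figure in the plan needs reproducing. The check sets the rules side by side and then counts the visits they govern.

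| Step | Screening | After first dose |
|---|---|---|
| Question asked | Attempt and ideation (12.1.8) | Ideation only (12.1.8, footnote g) |
| What opens the full C-SSRS | Positive answer to the screening query (12.1.8) | Positive ideation query (12.1.8, footnote g, SAP 10.4.3) |
| Criterion for action | Any lifetime attempt, or ideation by Question 4/5 (Exclusion 20) | Ideation by Question 4/5 (6.4, footnote g); 12.1.8 names an attempt but ties it to Question 4/5 |

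**Trace for a patient with an attempt since the last visit who denies ideation**
1. The ideation query is negative.
2. The full C-SSRS is therefore not done.
3. Questions 4 and 5 are never put.
4. No mandatory IMP stop, withdrawal or referral follows under Section 6.4, Section 12.1.8 or footnote g.
5. The SAP 10.4.3 listing holds ideation and C-SSRS results only, so the attempt does not appear there.

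**Does the 12.1.8 wording rescue it?** The sentence can be read in two ways. If Question 4/5 confirms both the attempt and the ideation, an attempt alone never qualifies. If it means an attempt, or else ideation confirmed by Question 4/5, an attempt does qualify, but no preceding question brings it to light, and the Section 6.4 list still has no attempt criterion. The screening paragraph has the same loose wording, but Exclusion 20 covers it there. Nothing plays that part on study.

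**Visits governed by the rule** (Protocol Sections 8.2.3, 8.2.5, 8.2.7, 8.3.1 and 8.3.2)
- Dosing visits after the first dose: Visits 4, 6, 8, 10, 12, 14, 16 = 7.
- Visits 17, 18, 19, 20, 21 = 5.
- Patient followed to Visit 21: 7 + 5 = 12 queries.
- Patient entering the extension at Visit 17: 7 + 1 = 8 queries.
- If all 34 randomized patients complete treatment: 8 × 34 = 272 (all leave at Visit 17) to 12 × 34 = 408 (all reach Visit 21). Queries at stabilization visits are extra.

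**Stopping IMP versus leaving the study.** Section 6.4 reserves mandatory study withdrawal for withdrawn consent and pregnancy, and puts Question 4/5 ideation under mandatory IMP discontinuation. Footnote g puts the same finding under study withdrawal.

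**The case against.** The best counter-argument is that Section 12.1.8 already names an attempt among its on-study triggers and requires referral and reporting through the SAE process, so the fault is only that Section 6.4 and footnote g do not repeat it. Moreover, the visit lists call the item a query for suicidality, and the form itself is not in the documents. There are also other routes. A general AE prompt is given at each visit, an attempt with medical consequences would be an SAE reported within 24 hours, the Study Physician and the DMC review safety, and interfering illness and a sponsor request are both on the mandatory IMP-stop list. An attempt reported as an AE appears in the SAP's AE listing. On the wording conflict, the protocol uses withdrawal loosely elsewhere: Section 12.3.7 withdraws tuberculosis cases from the study by reference to Section 6.4, which lists them under IMP discontinuation.

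Much of this limits the problem without removing it. The likeliest missed case is narrow: an attempt, probably interrupted or aborted and without medical consequences, in a patient who denies ideation and does not volunteer the event. The visit counts show how often the query is used; they do not count missed events, and the totals assume that all 34 patients complete treatment. A reported attempt is not lost to the AE data.

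What does not stand is the claim that these routes replace the rule. Section 12.1.8 and footnote g, the only definitions given, make it an ideation query. The seriousness criteria in Section 12.1.1.2 do not name an attempt. The general stops need judgement, and none requires referral to a mental healthcare professional.

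**Conclusion.** The concern holds. Once dosing has begun, no rule specific to suicidality makes a suicide attempt without reported ideation a reason to give the C-SSRS, stop IMP or refer. The gap applies at every scheduled query after the first dose: 12 per patient followed to Visit 21, and 8 per patient entering the extension at Visit 17. The conclusion rests on a literal reading of Sections 6.4 and 12.1.8 and footnote g, and on the query being what those texts say it is. How often the gap would matter cannot be estimated, because the documents give no attempt rate; with prior attempters excluded it is probably rare. It concerns patient safety and consistent conduct, and has no claimed bearing on sample size or the primary analysis. It should be corrected.

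**What to change.** 1. **Section 12.1.8, query:** at each query visit, ask about any suicide attempt since the last visit (active, interrupted or aborted, as in Exclusion 20) as well as ideation. Do the full C-SSRS on a positive answer to either, and change the gate in footnote g to match.
2. **Section 12.1.8 and footnote g, trigger:** reword to any suicide attempt, or suicidal ideation confirmed by Yes to Question 4 or 5.
3. **Section 6.4:** add suicide attempt to the mandatory IMP-discontinuation criterion.
4. **Consequence:** for patients already on study, bring footnote g and Section 12.1.8 into line with Section 6.4: stop IMP, refer at once, and continue with the PEOT visit and Observation Period follow-up. Section 6.4 already provides for that visit: "Subjects who withdraw from the study or discontinue IMP during the Treatment Period should complete the assessments outlined for Visit 17/PEOT".
5. **SAP Section 10.4.3:** update the gate and add the answer on attempts to the listing.

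The cost is wording in three protocol places and one SAP paragraph, one added question with a field to record it, and the amendment approvals that Section 15.5 requires. No new instrument or visit is needed.
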